Chronic pain is accompanied by a host of emotional, behavioral, and cognitive psychosocial consequences. At the same time, psychosocial factors contribute to chronic pain, including fear of movement and catastrophizing, maladaptive emotional and cognitive processes, and adverse life experiences. Treatment guidelines stress the importance of psychosocial aspects in pain management. Unfortunately, both patients and medical providers find it difficult to discuss psychosocial problems. The goal of this project is to remedy this critical problem by developing and pilot testing novel therapeutic interviews delivered by next-generation Virtual Humans (VHs) to help patients engage in discussions about pain-related psychosocial factors. In this IRB application, we will develop VH-assisted therapeutic psychosocial interviews specifically for chronic pain. Three Virtual Human interview scripts will be developed: One that facilitates participant disclosure of psychological distress, coping, medication usage, and stressful live events; one that mirrors this condition but includes explanations of how the mind contributes to chronic pain, and a control condition that asks about participants' medical history, medications, and chronic pain background. Adult patients who experience chronic musculoskeletal pain, are fluent in English, have no visual and cognitive impairment that would interfere with participation, have an average pain score of 4 or higher during the past week on a 0 to 10-point scale, and are receiving treatment for their chronic pain will be recruited through flyers from the Keck Medical School and invited to participate in a session with a Virtual Human at USC's Institute for Creative Technologies (ICT). Each patient who agrees to participate will come to ICT and will be assigned to one of the three VH conditions. The session at ICT consists of written informed consent followed by online questionnaires (e.g., demographics, mental and physical health, stressful live events, pain medication usage, coping), followed by the VH session, followed by post-session online questionnaires (e.g., satisfaction with the VH session), and then a brief structured interview with a research assistant about patients' experience with the VH. Patients will also be invited to participate in a brief online survey one month after the session with the VH at ICT. Patients will be compensated \$70 via Amazon gift card for the 1 1/2 to 2 hour session at ICT and an additional \$10 via Amazon gift card, if they agree to complete the online survey about one month after the study visit at ICT. Based on participant feedback (qualitative and quantitative), the Virtual Human interviews will be refined as necessary to improve the sessions.

Describe the inclusion criteria for enrollment.

Adult patients who experience chronic musculoskeletal pain (e.g., pain in the neck, back, arms, and legs) will be recruited via flyers from the Keck Medical School (e.g., the Keck Pain Center). Patients are eligible to participate if they (1) are 21 years or older, (2) experience chronic musculoskeletal pain (i.e., pain for at least three months), (3) are fluent in English, (4) have no visual/cognitive impairment that would interfere with participation in the study, (5) receive treatment for their chronic pain, and (6) report an average pain severity during the past week of 4

or greater on a 0 to 10 point scale, and (7) are willing to participate in a 1 1/2 to 2 hour session at USC's Institute for Creative Technologies.

Describe the exclusion criteria for enrollment.

1) younger than 21 years, (2) no chronic musculoskeletal pain, (3) not fluent in English, (4) visual/cognitive impairment that would interfere with participation in the study, (5) not in treatment for chronic pain, and (6) average pain severity during the past week lower than 4 on a 0 to 10 point scale, (7) not willing to participate in a 1 1/2 to 2 hour session at USC's Institute for Creative Technologies.

If there are any age, ethnic, language, or gender-based exclusion criteria, please provide justification.

Patients must be fluent in English and adults as the Virtual Human interview scripts are developed in the English language and for adults.

Research Objectives and Background

Describe the specific objectives or aims of the study and hypotheses or research questions.

The goal of this project is to develop three Virtual Human (VH) interview conditions for patients who experience chronic pain. Two of these VH conditions will focus on participants' disclosure of negative mood, psychological distress, coping with chronic pain, stressful life experiences, pain medication usage, and personality characteristics. The third condition is a control condition that focuses on the medical aspects of patients' chronic pain experience including their pain medication usage. In order to develop the best possible VH interviews, stakeholder feedback by patients is critical. We will, therefore, pilot test the three VH interviews with patients who experience chronic pain to get their qualitative (e.g., structured interview) and quantitative feedback (e.g., questionnaires) about their experience and how the VH interviews could be improved. In order to examine the best features of a Virtual Human coach, we will compare Virtual Humans that deliver the session either with a computer-generated voice or a voice recorded by a real person. Half of the patients in each of the three conditions will hear the computer-generated Virtual Human voice and the other half will hear the voice recorded by a real person. Patient feedback will tell us whether patients might prefer one Virtual Human voice over the other.

Chronic pain is accompanied by a host of emotional, behavioral, and cognitive psychosocial consequences. At the same time, psychosocial factors contribute to chronic pain, including fear of movement and catastrophizing, maladaptive emotional and cognitive processes, and adverse life experiences. Treatment guidelines stress the importance of psychosocial aspects in pain management. Unfortunately, both patients and medical providers find it difficult to discuss psychosocial problems. The goal of this project is to remedy this critical problem by developing and pilot testing novel therapeutic interviews delivered by next-generation

Virtual Humans (VHs) to help patients engage in discussions about pain-related psychosocial factors.

Provide a summary of the background of the study and explain how this research will contribute to existing knowledge. Describe previous work that provides a basis to show that the proposed research can be carried out without undue risk to human subjects. Include relevant citations.

Our team at the University of Southern California's Institute for Creative Technologies consists of world leaders in the development of Virtual Human technology for health research. ICT has successfully developed Virtual Human prototypes and conducted many research studies at USC that relate to the proposed project with minimal risk to participants.

Methods and Procedures - Prospective Studies

Describe in detail the design and methodology of the study. Provide a detailed description of the planned data collection, specific outcomes, and criteria for evaluation and endpoint definition. If applicable, include information on stratification or randomization plans. Include the frequency and duration of each activity and the total length of subject participation.

If patients volunteer to participate in this study, they will schedule an individual 1.5 to 2-hour session at USC's ICT. At ICT, they will first read and sign a study consent form before entering the study. They will also get a copy of the consent form to keep. The research team will answer any questions they may have about the study before patients decide to participate. Once patients have agreed to participate and signed the consent form, they will be asked to complete four parts of this study. These are:

- 1) an online general health and well-being survey (approx. 15-20 minutes),
- 2) an interview with a Virtual Human about their life with chronic pain (approx. 45-60 minutes)
- 3) an online questionnaire after their Virtual Human interview (approx. 15 minutes), and
- 4) an interview with research staff about their experience with the Virtual Human (approx. 15 minutes).

Patients' overall time commitment for this study is expected to be between 1 and 2 hours and they will be compensated with \$70 via Amazon gift card for their participation in this session at ICT.

Patients will also be invited to complete a brief (approx. 15 minutes) online questionnaire

(e.g., about their continued satisfaction with the Virtual Human session) about one month after the session at ICT that they can complete from their home computer. If patients agree to complete the survey, they will receive an additional \$10 via Amazon gift card.

Gift cards will be emailed to patients about 4 weeks after their participation in the ICT session and the one-month post ICT session online survey.

During their visit at ICT:

- 1) We will ask patients to complete different questionnaires pertaining to their demographics and medical background, their emotions, chronic pain management and medication usage, and stressful events. These questionnaires will be completed in an online survey before and after the interview with a Virtual Human and in the brief online survey about a month after the visit at ICT for the study.
- 2) Patients will also be asked to interact with a Virtual Human interviewer. This study has three different types of interviews, and patients will be assigned to one of them. In the course of this interaction, they will be asked to answer personal questions, such as about their emotions, stressful life experiences, how they cope with chronic pain, and their medical treatment and pain medication usage for chronic pain. The Virtual Human interview will be audio-recorded for analysis purposes.
- 3) At the end of the ICT study visit, we will ask patients to tell us about their experiences with the Virtual Human in a structured interview with our research staff. The goal of this interview is to learn how they felt about their interaction with the Virtual Human and if we can improve the interviews. This interview with research staff will also be audio-recorded for analysis purposes.

If patients do not want to be audio-recorded, they cannot participate in this research study.

Describe the statistical considerations for the study, how the sample size was determined, and how the results will be analyzed, if applicable.

Pilot studies typically consist of relatively small sample sizes and our proposed study sample consists of 35 to 50 patients. Given that this study will iteratively refine the Virtual Human interview scripts depending upon participant feedback, we will recruit up to 50 participants, if the Virtual Human scripts more need refinement. Patient feedback will be in the form of qualitative (e.g., a brief structured interview with a research assistant at ICT) and quantitative (e.g., standard questionnaires) data. These data will inform us whether the Virtual Human interview scripts function as intended, need improvement, and whether participants enjoyed the interaction with the Virtual Human. The majority of patients will be assigned to the two psychosocial Virtual Human conditions and fewer to the control condition.

Deception

Describe why the research cannot be carried out without deception.

The goal of this research is to develop Virtual Human interview scripts for patients with chronic pain. Prior research has shown that patients are often reluctant to open up about psychosocial aspects (e.g., anxiety, depression, stressful life events, pain medication usage) with their healthcare providers or other people. We are developing these Virtual Human-assisted interviews to remedy this problem and give patients a space to talk about these issues. As part of the development process of the scripts and potential necessary refinement, the Virtual Human cannot be fully automated yet but requires a research assistant to deliver the Virtual Human lines in real-time. Telling patients before the Virtual Human study session that the Virtual Human is controlled a real person would be counterproductive to patients' feeling that they can talk openly with a computer-generated character. ICT has successfully conducted similar studies that involved participant interaction with a human-controlled Virtual Human. We will debrief participants after the structured interview with the research assistant and are attaching the debriefing statement.

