Official Grant Title: Virtual Human Technology for Patients with Chronic Pain

Working Title: Virtual Human–Delivered Interviews for Patients with Chronic Pain: Feasibility, Acceptability, and a Pilot Randomized Trial of Standard Medical, Psychosocial, and Educational Interviews

NCT #: 04349033

Date: October 15, 2021

Statistical Analysis Plan

To test our aim (whether interviews affected pain-related outcomes about one month later), we will conduct intent-to-treat (ITT) analyses using data from all patients, accommodating missing values on outcomes using maximum likelihood parameter estimation. Two-way repeated-measures ANOVAs with one between-subjects factor (experimental condition) and one within-subject factor (time) will be tested using linear mixed effects models (using the MIXED procedure in SAS 9.4; Cary, NC). Analyses will focus on time by group interactions (indicating group differences in change from baseline) for two specific comparisons: 1) Psychosocial vs. Standard; and 2) Educational vs. Standard. We will also inspect changes from baseline within each of the three experimental conditions separately using post-hoc contrasts. We will include VH voice (human vs. computer) as a covariate in all models and include age and education as covariates in sensitivity analyses.

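### Does refining the interview scripts during recruitment, with no last-change point, undermine the SAP's all-patient contrasts?

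*Protocol*

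**What the plan says.** The answer on statistical considerations, under the Protocol's Methods and Procedures - Prospective Studies, gives a sample of 35 to 50 patients and justifies the upper end by script development: "Given that this study will iteratively refine the Virtual Human interview scripts depending upon participant feedback, we will recruit up to 50 participants". The extension is conditional: "we will recruit up to 50 participants, if the Virtual Human scripts more need refinement". It puts most patients in the two psychosocial conditions and fewer in the control, without a ratio. No date, patient number or version marks the end of refinement.

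Elsewhere the Protocol presents refinement as the purpose, and as contingent. Research Objectives and Background says "In order to develop the best possible VH interviews, stakeholder feedback by patients is critical" and pilots all three interviews, the control included. The Deception section speaks of "As part of the development process of the scripts and potential necessary refinement". The opening summary also refines the interviews only as needed.

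The SAP's aim is to test "whether interviews affected pain-related outcomes about one month later". For this, "we will conduct intent-to-treat (ITT) analyses using data from all patients". The model has condition, time and their interaction, with voice as a covariate and age and education added in sensitivity analyses. Script version does not appear.

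**The concern.** The Protocol links enrolment beyond 35 to continuing refinement, so the later patients may be the ones recruited while the scripts are still moving. A material change could come very late, and the all-patient contrast would then rest mostly on superseded scripts. If those were weaker than the final one, a null result would be more likely even though the final script works. If they were stronger, the result would flatter it. A reader who takes the contrast as evidence about the finished interview could be misled, and nothing in the SAP says which version or mix of versions the estimate describes. A freeze early in enrolment looks like a cheap remedy: it seems to need no extra patients and no change to the model.

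**Working it through.** **Inputs.** From the documents: 35 to 50 patients, all analysed, and two contrasts against Standard. Assumed, because the documents give no figure: a 2:2:1 split (20/20/10 of 50, or 14/14/7 of 35), one material script change, complete follow-up, and a final-script effect d of 0.5, 0.8 or 1.0 change-SD. The early script is assumed to have a fraction r of that effect, with r from 0 to 1.25. The 35 to 50 range rests on no power calculation, so there is no planned figure to reproduce.

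**Step 1: how far the average can lie from the final effect.** Let f be the share of patients on the early script. Then

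pooled / final = f × r + (1 − f).

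| Last change | f | r = 0 | r = 0.5 | r = 1 | r = 1.25 |
|---|---|---|---|---|---|
| After patient 35 of 50 | 35/50 = 0.70 | 0.30 | 0.65 | 1.00 | 1.175 |
| After patient 15 of 50 | 15/50 = 0.30 | 0.70 | 0.85 | 1.00 | 1.075 |

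The gap can go either way, and it is zero if the versions do not differ.

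**Step 2: is the test still valid?** A two-period simulation (20,000 runs, 20 vs 10, two-sample t-test on change scores as a stand-in for the mixed model) had no effect of any version and a period trend of 0, 0.5 or 1 SD. With the ratio constant over time (10:5 in each period), type I error was 0.051, 0.044 and 0.028, so it was not inflated. With an assumed drift in the ratio (6:8 early, 14:2 late) it was 0.051, 0.089 and 0.187. Validity therefore needs assignment that is random, concurrent and at a steady ratio. Nothing in either document suggests drift.

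**Step 3: what an early freeze would buy.** Power is from the noncentral t, two-sided 5%, with SE = √(1/n₁ + 1/n₂) and df = N − 4 (three conditions and voice). For 20 vs 10, SE = √(1/20 + 1/10) = 0.387 and df = 46. For 14 vs 7, SE = √(1/14 + 1/7) = 0.463 and df = 31. With recruitment ending at 35 after a freeze at 15, f = 15/35 = 0.43, and at r = 0.5 the ratio is 0.43 × 0.5 + 0.57 = 0.79.

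| Scenario | pooled / final | Power, d = 0.5 / 0.8 / 1.0 |
|---|---|---|
| r = 0.5, late change, N = 50 | 0.65 | 0.130 / 0.260 / 0.376 |
| r = 0.5, early freeze, N = 50 | 0.85 | 0.189 / 0.405 / 0.575 |
| r = 0.5, early freeze, N = 35 | 0.79 | 0.130 / 0.260 / 0.376 |
| r = 1, N = 50 | 1.00 | 0.244 / 0.525 / 0.715 |
| r = 1, N = 35 | 1.00 | 0.182 / 0.388 / 0.553 |

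The third row matters most. The Protocol goes to 50 only if the scripts need more work. Scripts frozen at patient 15 remove that reason, and at N = 35 the gain over a late change vanishes. At r = 1.25 and d = 0.8, power at N = 50 is 0.661 with a late change and 0.585 with an early one, so the freeze lowers it.

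**Step 4: precision.** The 95% half-width is t(0.975, N − 4) × SE.

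- All 50 (20 vs 10): 2.013 × 0.387 = 0.78 change-SD.
- All 35 (14 vs 7): 2.040 × 0.463 = 0.94. The same figure holds for the 35 patients who follow a freeze at 15 of 50.
- The 15 patients after a change at patient 35 (6 vs 3): 2.201 × √(1/6 + 1/3) = 2.201 × 0.707 = 1.56.

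An analysis restricted to the final version is thus never more precise than the all-patient one, and after a late change it is close to uninformative.

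**Step 5: cost to development.** At 2:2:1, the first 15 patients are 6, 6 and 3. The control script would be refined on about three people, split between two voices.

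**The case for a change.** The best case for acting is that the SAP's working title calls this a randomised pilot and the SAP tests an effect on outcomes, so readers will want to know which interview was tested. Without a record of versions, a null for the final script cannot be told from a null for early drafts. The record would be cheap: one variable and one table of counts. The recordings could even help to recover it afterwards, since "The Virtual Human interview will be audio-recorded for analysis purposes" and "If patients do not want to be audio-recorded, they cannot participate in this research study".

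Most of this is fair as advice on reporting. Describing the result as an average over the versions delivered, with counts by version and condition, would make the paper clearer. But it would leave the analysis set, the model, the estimates and the conclusions as they are, and the team can do it at write-up without an amended SAP.

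A second objection also stands in part. Calling the contrast valid presumes random, concurrent assignment, yet the Protocol says only that patients are assigned, and randomisation appears only in the SAP's working title. That is a condition on the conclusion here. A last-change point would not supply it.

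**Conclusion.** No change to the plan is called for. The textual observation is correct: refinement may run through recruitment, no end point is set, and the SAP does not distinguish versions. What follows is a limit on interpretation. The SAP asks whether the interviews affected outcomes, and an all-patient average over the versions delivered answers that. The effect of the final script alone is a different quantity, which the SAP does not claim to estimate.

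The departure from the final-script effect could be nil, or the contrast could be 30% to 118% of that effect under the late-change assumptions. The documents give no basis for choosing within that range. Freezing the scripts is a fair trade-off that the team has resolved in favour of development, and its gain in power depends both on enrolling 50 regardless and on early scripts being weaker. At best the half-width remains 0.78 change-SD, so the pilot would not be conclusive either way.

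This rests on three assumptions: the SAP's patients are the same 35 to 50 used for refinement (plausible, since the conditions match, but not stated), assignment is random and concurrent, and the ratio stays constant across versions.

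### As worded, the age and education sensitivity analyses cannot show whether imbalance in those factors affects the time-by-group contrasts

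*Protocol*

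**What the plan says.** The SAP's single section sets the question as "whether interviews affected pain-related outcomes about one month later". It fits linear mixed models by maximum likelihood to all patients and bases inference on "time by group interactions (indicating group differences in change from baseline", for Psychosocial against Standard and Educational against Standard. Voice is a covariate throughout. Age and education are added only in the sensitivity models. No interaction of a covariate with time is mentioned.

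On allocation, the SAP's working title has "Pilot Randomized Trial of Standard Medical, Psychosocial, and Educational Interviews". The protocol summary has "Each patient who agrees to participate will come to ICT and will be assigned to one of the three VH conditions", and the description of the visit under Methods and Procedures has "This study has three different types of interviews, and patients will be assigned to one of them". The statistical considerations add "The majority of patients will be assigned to the two psychosocial Virtual Human conditions and fewer to the control condition" and give the size as "our proposed study sample consists of 35 to 50 patients". The form's prompt reads "If applicable, include information on stratification or randomization plans". The answer beneath it gives no sequence method, numeric ratio for the interview conditions, or concealment. Voice alone has a stated split, even within each condition.

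**The concern.** A sensitivity analysis is useful only if it could have given a different answer. Readers will take agreement between the main model and the age-and-education model as evidence that the contrasts against Standard do not reflect older or less educated patients in one arm. If the covariates enter as main effects only, the two models agree by construction, and the agreement says nothing about imbalance. Arms are small here and Standard is planned to be the smallest, so noticeable gaps in age or education can arise by chance even under proper randomization.

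**Working it through.** The plan gives no figure to reproduce: the sample size is a pilot range with no alpha, power, SD or dropout. The check is of the model.

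**1. Algebra.** For patient i in group g at visit t (0 = baseline, 1 = one month), with x = age and education as main effects:

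Y(i,t) = m + a(g) + T·t + d(g)·t + B·x(i) + c·voice(i) + b(i) + e(i,t)

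Subtracting visits: Y(i,1) − Y(i,0) = T + d(g) + e(i,1) − e(i,0).

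The term B·x(i) is the same at both visits and drops out, as does voice. With both visits observed, the estimate of d for Psychosocial is the difference in mean change from Standard, with or without x. If x also interacts with time, with coefficient Q, the change becomes T + d(g) + Q·x(i) + error, and d is then adjusted for x.

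**2. Complete data, simulated.** Random-intercept models of group x time plus voice were fitted to arms of 20/20/10, with and without main-effect age and education. The largest difference in the Psychosocial-by-time estimate was 1e-14 over 200 trials. In four further settings of 300 trials (20/20/10 and 14/14/7, age slope 0.2 and 0.4, age gap 0.5 SD) it was 0.0000.

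**3. Missing follow-up, same four settings, 20% missing (assumed).** The mean difference between the two models was −0.001 to 0.001. The largest shift in a single trial was 0.17 SD, in either direction. The average is zero although an age gap was built in, so the movement is not a correction for age.

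**4. Size, by assumed example.** Psychosocial is 0.5 SD older than Standard, change shifts by 0.2 to 0.4 SD per SD of age, and there is no true effect. Expected error = 0.5 × 0.2 = 0.10 to 0.5 × 0.4 = 0.20 SD, unchanged by main-effect age. With the time interactions the expectation is 0. Simulated means were −0.07 to 0.05 (Monte Carlo SE 0.02 to 0.03).

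**5. Separate simulation.** 250 trials per row, 20/20/10, true effect zero, no voice term, complete data. Entries are the mean Psychosocial-by-time estimate in the simulated outcome's units (Monte Carlo SE about 0.03), with the rejection rate at 5%.

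| Assignment depends on | No covariates | Main effects | Covariates x time |
|---|---|---|---|
| Nothing (random) | −0.047, 4% | −0.047, 4% | −0.041, 6% |
| Age | 0.509, 18% | 0.509, 18% | −0.033, 5% |
| An unmeasured factor | 0.516, 22% | 0.516, 22% | 0.522, 28% |

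**6. How often a chance gap arises.** Under simple randomization at 2:2:1 (assumed), the SE of an age difference in SD units is sqrt(1/20 + 1/10) = 0.387 at N=50 and sqrt(1/14 + 1/7) = 0.463 at N=35. A gap of at least 0.5 SD in either direction has z = 0.5/0.387 = 1.29, P = 0.197, and z = 0.5/0.463 = 1.08, P = 0.280.

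**7. Cost of the unstated ratio, in precision.** Assumptions: two-sided 5%, 80% power, noncentral t with N − 4 df, SE = sqrt(1/n1 + 1/n0), no loss. The detectable difference in SDs of change is 0.997 (17/17/16) to 1.108 (20/20/10) at N=50, and 1.207 (12/12/11) to 1.339 (14/14/7) at N=35.

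**The case against.** Several counter-arguments have force.

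- **The SAP does not say main effects.** It may have meant interactions with time. If so, one sentence settles the point. Main effects are the plain reading of the wording, but they remain an assumption.
- **Cancellation is not exact when follow-up is missing**, and the SAP expects missing outcomes. This stands for single estimates (up to 0.17 SD). The average shift was still 0.00. Other missing-data patterns could give other figures.
- **Under random assignment, chance imbalance is already in the standard error.** This stands. In 8,000 trials per setting (20/20/10 and 14/14/7, age slope 0 to 0.4), the unadjusted change contrast rejected 4.7% to 5.6% of the time. The chance gaps of 20% and 28% therefore do not undermine the primary analysis. They only show that the sensitivity check will often have something to examine.
- **Time interactions do not repair selection on unmeasured factors.** This stands: the bias was 0.516 with main effects and 0.522 with the interactions.
- **The missing ratio matters little.** It moves the detectable difference by 1.108 − 0.997 = 0.11 at N=50 and 1.339 − 1.207 = 0.13 at N=35. The planned range of N moves it by 0.21 to 0.23. No power claim is made.

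A reader might go further and infer that the trial was not randomized, or that age and education were meant to stand in for a missing randomization. The documents support neither. The working title says randomized, and the intent-to-treat wording and the experimental-condition factor fit that. The form asks for a plan only if applicable. Nothing suggests that the ratio changed during script refinement. The SAP never gives the covariates the role of a substitute for randomization.

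**Conclusion.** The point holds for the form of the covariates and is minor. If age and education enter as main effects, the planned sensitivity analysis returns the main estimate exactly with both visits observed, and on average with 20% missing. It cannot show whether imbalance in either factor affects the two contrasts against Standard. In the assumed example, an error of 0.10 to 0.20 SD would pass through unseen. That size depends on the assumed age gap and slope, which the documents do not give. The cancellation with complete data depends on neither.

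This is no finding of bias in the primary analysis. The silence on ratio, method and concealment is a reporting gap in the public text, and it does not show that assignment was non-random.

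**What to change.** In the SAP's sensitivity models, keep the main effects of age and education and add age x time and education x time. In the planned SAS procedure this adds two terms to the MODEL statement. State that the adjustment covers these two factors only.

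The cost is about 2 df if education is numeric, and more if it is categorical. Precision may fall slightly when these factors do not predict change: in the simulations under random assignment, adding both to the change model altered the SD of the estimate by about −7% to +3%. No new data are needed, and N, arms and primary model stay as they are.

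As a separate reporting step, state in the protocol's statistical considerations and in the SAP how patients are or were allocated, the numeric ratio across the three interview conditions, and whether the next assignment was concealed from enrolling staff. This takes a few sentences and implies no change of design.
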